3.1 Type of Trial

The trial is a double-blind, randomized, placebo-controlled, parallel group trial investigating the efficacy and safety of Panhematin[™] for preventing acute attacks in at least 20 patients with well-documented acute porphyria (AIP, HCP or VP). These patients will (1.) have had frequent attacks in the past, with symptoms such as abdominal, back and/or limb pain and diagnosed after exclusion of other causes, and (2.) be on hemin prophylaxis for prevention of frequent attacks. Although clear guidelines have not been developed, it is expected that patients will have had 6 or more attacks in one year before starting hemin prophylaxis. This would be considered justification for a preventive regimen of hemin on clinical grounds. Most patients on hemin prophylaxis are given a single dose once weekly. However, other prophylactic regimens are effective in some patients, such as twice weekly infusions or a series of 3-4 infusions at monthly intervals. Giving only one blinded infusion may not be meaningful for a patient for whom more than a single infusion is needed to prevent attacks. Therefore, patients will

be offered the number of blinded infusions they usually are given within approximately one week for prophylaxis. All infusions for each patient will be either Panhematin[™] or placebo. An interim analysis will be carried out after completion of ~10 patients to assess progress and possibly adjust the sample size. The trial consists of the following:

- A screening visit to determine eligibility and obtain informed consent
- A treatment visit for administration of one or more double blind prophylactic doses of Panhematin[™] or placebo, corresponding to each patient's usual prophylactic regimen. Depending on the regimen, this visit may be completed in one day or after the number of days corresponding to their usual prophylactic regimen over approximately one week.
- Follow up visit at 1, 2, 3, and 4 weeks to assess response to the infusion of Panhematin[™] or placebo. These visits will be in person or by telephone.
- Additional visits may be scheduled if needed, for example for treatment of symptoms.
- Follow-up visits 3 and 6 months after the end of treatment either in person or by telephone

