 - ii. Total fecal porphyrins <400 ug/g dry weight or <2-fold increase (relative to ULN of 200 ug/d dry weight
 - c. Erythrocyte HMBS/PBGD activity deficient in ~90% of cases
 - i. Activity should be below the lower limit of normal, or <60% of the normal mean for the laboratory; this enzyme activity may be falsely low due to improper sample handling or physiologically increased when erythrocyte turnover is increased.
- 3. Molecular findings known:

a. Disease-causing mutation in *HMBS* (also known as *PBGD*) in >95% of cases.

b. Biochemical criteria will suffice if no mutation can be identified.

4. Previous acute attacks of porphyria, consisting of symptoms such as abdominal, back and/or limb pain, diagnosed by the investigator as caused by porphyria after exclusion of other causes, and currently on a prophylactic regimen of Panhematin[™].

Hereditary coproporphyria (HCP):

1. Clinical features – a history of consistent clinical features such as acute attacks of abdominal, back and/or limb pain

- 2. Biochemical findings:
 - a. A marked increase in urinary or serum PBG and/or in urinary coproporphyrin III before treatment with Panhematin™.
 - i. For urinary and serum PBG, same as for AIP (see above)
 - ii. For urinary total porphyrins: >450 nmol/24 hours or g of creatinine, or more than 1.5-fold increase (relative to ULN of 300 nmol/24 hours or g of creatinine
 - b. Normal or only slight increases in plasma porphyrins.
 - Plasma porphyrins <5 ug/dL, or <5-fold increase (relative to ULN of 0.9 ug/dL); fluorescence scanning at neutral pH should show no peak or a small peak at ~620 nm. *Note:* this criterion applies to HCP patients without skin lesions. Skin lesions are rare in this disease, but if present are often accompanied by substantial increases in plasma porphyrins. An exception will be made for this criterion in such cases.
 - c. A substantial increase in fecal porphyrins, with a predominance of coproporphyrin III.
 - i. Total fecal porphyrins >400 ug/g dry weight or >2-fold increase (relative to ULN of 200 ug/g dry weight, with a predominance of coproporphyrin III and a coproporphyrin III/I ratio >1.5
- 3. Molecular findings known:
 - a. Disease-causing mutation in *CPOX* in >95% of cases.
 - b. Biochemical criteria will suffice if no mutation can be identified.

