6.1.1 Visit 1 – Screening and Enrollment

Patients will be fully informed about the purposes and procedures of the study, orally and in writing, and asked to sign an informed consent form approved by the IRB, which describes study procedures and the risks and potential benefits of the study. Patients will be screened for eligibility and enrolled at Visit 1. Any additional studies needed to determine eligibility will be done at that time.

Procedures:

After enrollment each subject will be allocated a unique study enrollment number. If the inclusion and exclusion criteria (see below) are satisfied, the patient will be randomized during the screening visit or before and assigned a unique study randomization number. The following will be performed and recorded in the CRF:

- 1. Checks of Inclusion and Exclusion Criteria.
- 2. Demographic Information, to include:
 - Date of Birth
 - Sex
 - Race and ethnicity

- 3. History, to include:
 - Year of first porphyria attack
 - Number of attacks during the past 6 months
 - Attacks related to the menstrual cycle or not
 - Attacks related to other precipitating factors (harmful drugs, nutritional alterations, etc. or not
 - Time of onset of the most recent attack
 - Previous treatment with Panhematin™
- 4. Concomitant illnesses
- 5. History of allergy
- 6. Concomitant medications
- 7. Use of opioid agonists during the previous 6 months
- 8. Physical Examination, including:
 - a. Body height and weight
 - b. Vital Signs
- 9. Electrocardiogram, if clinically indicated
- 10. Recording of porphyria-related signs and symptoms
- 11.Blood samples will be drawn for testing, to include erythrocyte PBGD activity, serum or plasma PBG and porphyrins, complete blood counts, and metabolic and hepatic panels
- 12.Urine sample will be collected for assessment of urine ALA, PBG, and porphyrins.
- 13. Fecal sample will be collected for porphyrins.
- 14.Blood sample for DNA isolation and mutation analysis (unless done previously). This is now considered standard of care diagnostic testing for porphyrias, and is widely available. A separate consent form for this testing will be provided only if required by the testing laboratory.
- 15. Urine pregnancy tests (for females of childbearing potential only).

6.1.2 Visit 2:

Procedures:

The following will be performed and recorded in the CRF (at time of treatment):

- 1. Concomitant medications, and any changes not recorded previously
- 2. Vital Signs

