12.3 Statistical Methods

All tests for significance will be two sided at the 5% significance level and accordingly 95% confidence intervals will be determined.

The main clinical efficacy variable, the occurrence or nonoccurrence of an acute attack each of the 4 weeks following test infusion, will be analyzed by logistic regression with treatment as a factor and drug dose as a covariate. Data for any post randomization exclusions will be listed and the possible impact assessed.

Use of Panhematin[™] and opioids for treatment of porphyria symptoms during the 4 weeks following treatment will be analyzed by exact two sample Wilcoxon tests or by Fisher's exact test.

Supplementary analyses of the role of demographic and clinical features will be performed.

Adverse events will be coded and analyzed descriptively.

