12.4 Sample size determination

The power to detect a treatment-related difference in frequency of attacks and other measurements increases with the magnitude of the differences that are induced by treatment. A prior case series with cross over from a pre-existing

control period to open label use of heme arginate to prevent frequent attacks showed a substantial effect in some patients, but little effect in others. That study suggests that a sample size of 20 should be sufficient. However, the previous study may not be useful in assessing sample size for the current study, which is of a different design. Therefore, an interim analysis is planned in this study after the first 10 subjects. The biostatistician will unblind the data for this analysis, but blinding will be preserved for all others.

The sample size needed to have 80% power to reject the null hypothesis of no effect using the two-sample comparison of proportions at the 5% significance level will be determined based on the initial sample. For instance, if the probabilities of recurrence are 0.8 and 0.2 in the control and treatment groups respectively, the power to detect with 20 patients (10 patients per group) is 80%. However, if the treatment group chance of recurrence is 0.38, the estimated sample size is 40 (20 patients per group). If the estimated sample size is 20 or less the trial will stop after 20 patients have completed; if it is up to ~40, consideration will be given to increasing the number of completed patients to 40; if it greatly exceeds 40 the trial will continue until 20 patients have been completed. If it is not feasible to reach a target sample size, or if it is not even feasible to find enough patients to have 80% power for establishing clinical efficacy, the trial will continue and stop when 20 patients have completed.

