12.5 Interim analyses

An interim analysis is planned after completion of 10 subjects, to determine a reasonable estimate of the variance, as stated above in 12.4. Given the change in inclusion criteria, a logistic model will be fit to assess the change in recurrence rate by dose. We do not, however, expect that the dose or regimen effect will be statistically significant or have a substantial effect on the outcome.

13. Ethical considerations

The study will be conducted in accordance with accepted standards for human studies, including the Declaration of Helsinki. The study will be approved by the IRB at UTMB, as will changes made in study documents as appropriate.

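### The primary model spends its one covariate on drug dose, which 12.5 expects not to matter, and leaves out the baseline attack count that Visit 1 records

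*Combined protocol and SAP*

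**What the plan says.** - **Primary model (12.3).** Occurrence of an attack in each of the 4 weeks "will be analyzed by logistic regression with treatment as a factor and drug dose as a covariate". No other covariate is named. Demographic and clinical features are left to supplementary analyses that are not specified further.
- **Expected effect of that covariate (12.5).** "We do not, however, expect that the dose or regimen effect will be statistically significant or have a substantial effect on the outcome". The only reason given for modelling dose is a change in the inclusion criteria.
- **Baseline attack history (6.1.1).** Visit 1 records "Number of attacks during the past 6 months". The listed history items do not include the attack rate before prophylaxis began.
- **Population.** In 3.1, "it is expected that patients will have had 6 or more attacks in one year before starting hemin prophylaxis". The criteria in 4.3 require current Panhematin prophylaxis and "Previous acute attacks of porphyria, consisting of symptoms such as abdominal, back and/or limb pain, diagnosed by the investigator as caused by porphyria", with no minimum number.
- **Allocation (5.7).** Randomisation is in blocks of 4, and no stratification factor is stated.
- **Sizing (12.4).** 80% power "using the two-sample comparison of proportions at the 5% significance level", without a covariate, for example 0.8 v 0.2 with 10 per group.

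**The concern.** The outcome is whether a patient has another attack, so how often that patient has been having attacks is a natural candidate for adjustment. The plan gives its single covariate to a quantity that it expects to be uninformative, and leaves out one that it already collects.

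Dose is also undefined as a covariate. Under 5.1 the dose per kg is 4 mg/kg except where the 313 mg cap applies, so mg/kg hardly varies and mg mostly follows body weight. The number of infusions is one for most patients (3.1). Hemin actually received is zero on placebo and so nearly collinear with treatment.

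With 10 patients per arm and no stratification, nothing in the design or the primary model addresses a chance imbalance in attack frequency. At stake are some power and some robustness in a very small trial.

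**Working it through.** **Inputs.** Two-sided 5% level (12.3); recurrence 0.8 v 0.2 at 10 per group and 0.8 v 0.38 at 20 per group (12.4); 1:1 allocation (5.7). The prognostic strength of attack frequency is not in the documents. It is assumed, as an odds ratio (OR) per SD from 1 (none) to 5, and up to 7.4 in a second check.

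**Step 1: the plan's own figures.** Pooled normal approximation, with p̄ the mean of the two rates:

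power = Φ{[p1 − p2 − 1.96·√(2p̄(1−p̄)/n)] / √[(p1(1−p1)+p2(1−p2))/n]}

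- 0.8 v 0.2, n = 10: (0.6 − 1.96 × 0.2236)/0.1789 = 0.904, power 0.817. Enumerating the Pearson test exactly gives 0.805.
- 0.8 v 0.38, n = 20: (0.42 − 1.96 × 0.1555)/0.1406 = 0.819, power 0.794. The required n is 21 per group, or 42 against the stated 40.

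Both figures are reproduced, for an unadjusted comparison.

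**Step 2: swapping the covariate, Firth penalised likelihood-ratio test.** Simulated trials at N = 20, marginal rates fixed at 0.8 v 0.2 (0.5 v 0.5 for type I error), standard normal covariate, no interaction with treatment. Ranges are the spread over repeat runs.

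| Covariate in the model | Power |
|---|---|
| No prognostic value (stands for dose) | 78-80% |
| Attack frequency, OR 1 per SD | 79-80% |
| OR 2 | 82% |
| OR 3 | 84-86% |
| OR 5 | 89% |

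Type I error is about 4-5%. With 4,000 trials per case the Monte Carlo standard error near 80% is √(0.8 × 0.2/4000) = 0.6 points, so differences of about 1 point are within noise.

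**Step 3: second check, ordinary likelihood-ratio test recalibrated to a true 5% size.**

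| OR per SD | N = 20, dose | N = 20, frequency | Difference | N = 40, dose | N = 40, frequency | Difference |
|---|---|---|---|---|---|---|
| 1.0 | 0.798 | 0.789 | −0.009 | 0.794 | 0.792 | −0.002 |
| 1.6 | 0.803 | 0.817 | +0.014 | 0.788 | 0.806 | +0.018 |
| 2.7 | 0.793 | 0.847 | +0.054 | 0.782 | 0.854 | +0.072 |
| 7.4 | 0.796 | 0.883 | +0.087 | 0.786 | 0.923 | +0.137 |

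The dose term itself costs little: 0.5 to 2 points at N = 20 against treatment alone. Most of any loss comes from the unused place in the model.

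**Step 4: dependence on the test.** At N = 20 with a Wald test, power over the same four ORs is 0.56 / 0.56 / 0.56 / 0.57 with dose and 0.57 / 0.54 / 0.51 / 0.36 with frequency, so the swap then does harm when frequency is prognostic. The uncalibrated ordinary likelihood-ratio test has true size 0.066-0.067 with dose and 0.066-0.101 with frequency. Near-separation (a coefficient above 8 in absolute value) occurs in about 20% of trials with treatment alone and 21-46% with frequency. Section 12.3 names no test for the treatment term.

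**The case against.** **No prognostic strength is documented.** A reader might infer that the plan demonstrably gives power away. The documents do not support that: the ORs above are assumptions, and at no effect there is nothing to gain. This objection stands and limits the point to a range.

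**The recorded count is not the frequency in 3.1.** Section 3.1 refers to the year before prophylaxis. Patients must currently be on Panhematin (4.3), and most have been on a preventive regimen for a long time (3.2), so the 6-month count is largely of attacks on treatment. It may be low, vary little and predict attacks on placebo poorly. This also stands, and is the main downside of the fix.

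**Dose has a rationale.** Regimens differ in the number of infusions, and needing more may reflect severity. That is a fair reason to look at dose or regimen, but a descriptive analysis can serve it, and 12.5 itself expects little effect.

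**Attack history is not shut out altogether.** Supplementary and exploratory analyses of clinical features could include it, although the count is not named there. Nor can one say that the pre-prophylaxis rate is missing from the CRF: the form is not in the documents, and 6.1.1 merely does not list that item.

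**Eligibility.** A reader might infer that 4.3 lets infrequent attackers dilute the trial. If a quarter of entrants had a 20% risk in either arm, the control rate would be 0.75 × 0.8 + 0.25 × 0.2 = 0.65, and the Step 1 formula gives (0.45 − 1.96 × 0.2211)/0.1969 = 0.085, power 53% instead of 82%. That proportion has no source. Section 3.1 states an expectation and says that clear guidelines are lacking. A patient who is now quiescent could still have had six attacks in the year before hemin. The 53% is illustrative only, not a loss that any change here recovers.

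**Conclusion.** The point holds in limited form. The only covariate in the primary model is one that the plan expects to be unimportant, and a baseline attack count already collected is left out. The effect of using the count instead, at N = 20 and 0.8 v 0.2, runs from at most about 1 point lost if it is not prognostic to about 9 points gained at an OR of 5 per SD. In the recalibrated check at N = 40 (0.8 v 0.38), it runs from nil to about 14 points at an OR of 7.4.

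This rests on an assumed prognostic strength, a normally distributed covariate, no treatment-by-covariate interaction, and a test suited to the sample size. Under a Wald test the conclusion reverses, so the covariate and the test must be changed together. The difference between 3.1 and 4.3 on attack history is a matter of wording to reconcile, with no power figure attached.

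**What to change.** 1. In 12.3, replace drug dose by one pre-specified baseline covariate on a single time base for all patients: log(1 + number of attacks in the past 6 months).
2. In the same sentence, state that treatment is tested by a Firth penalised likelihood-ratio test, not a Wald test.
3. Move dose or regimen to a descriptive analysis, and define it there (mg, mg/kg or number of infusions).
4. If the count for the 12 months before prophylaxis is preferred, collect it for every patient on one CRF line and use it alone. Do not fill gaps with the 6-month count: the two differ in duration and in treatment status.
5. Reconcile 3.1 and 4.3, so that the attack history expected of patients and the one required of them are stated consistently.

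**Cost.** SAP wording, and one CRF line only if step 4 is taken. The model keeps the same number of parameters. The risk is that the 6-month count proves weakly prognostic, in which case little is gained and at most about a point of power is lost.

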3.3 Treatment of Subjects and Rationale for Treatment

Panhematin TM 4 mg/kg will be reconstituted with 25% human albumin ⁵⁰ and infused over a 1 hour period. The amount of albumin is based on achieving a 1:1 molecular ratio for hemin and albumin 43,50 . Product labeling suggests that

Panhematin[™], after reconstitution with sterile water, be infused within 15 minutes. After reconstitution with albumin, an infusion time of 1 hour is based on guidelines for infusion of the amount of human albumin used for reconstitution. The longer infusion time of 1 hour is acceptable given the enhanced stability of hemin in the presence of albumin, and based on experience of investigators in the Porphyrias Consortium ⁹.

Glucose infusions will be permitted during the study for treatment of acute attacks. Its use will be recorded but will not be specified by the study. For treatment of acute attacks, Panhematin[™] product labeling suggests an initial trial of glucose at a dose of 400 grams daily, whereas a dose of 300 grams daily as 10% glucose is generally accepted ^{9,68-70} and a higher dose given as 10% glucose may increase the risk of fluid overload and hyponatremia. Smaller amounts (e.g. 200 grams as 2L 5% glucose in saline) have been recommended for meeting fluid, electrolyte and caloric needs, but not as an alternative to hemin therapy ⁷¹. There are no guidelines or published experience for glucose loading for prevention of attacks, but based on expert experience the impression is that it is not very effective and may lead to unwanted weight gain.

Symptomatic treatment, including opioids, needed to control pain and other symptoms during an attack that occurs during the study will be recorded. Use of medications needed to control chronic symptoms, including pain, will also be recorded.

4. Trial Population

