5.3 Timing of administration of Panhematin[™] or placebo

Treatment with Panhematin[™] or placebo should be given within ±2 days of the time a prophylactic dose or series of doses would have been administered. Panhematin[™] is FDA approved at the dosage level used in this study.

It is recommended in product labelling that Panhematin[™] be given once or twice daily. Therefore, in this study a dose of Panhematin[™] will not be given within 12 hours of a previous preventive dose of active study drug. If an attack occurs within 12 hours of the study dose of Panhematin[™] or placebo, open label treatment with Panhematin[™] will be delayed until 12 hours after the last study dose of Panhematin[™] or placebo. If it considered clinically necessary to start open label Panhematin[™] for treatment of the attack in less than 12 hours, the first therapeutic dose for the attack will be blinded, and will be Panhematin[™] if the patient was randomized to placebo, and will be placebo if the patient was randomized to Panhematin[™]. Whether active drug or placebo is given in this instance will be determined by the Pharmacy, where 1-2 individuals will not be blinded.

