5.4 Glucose administration

Glucose loading will be permitted for treatment of acute attacks during the study at the discretion of the patient's physician. No particular amount or regimen will be required during participation in this study, although a recommendation may be made to treat intravenously with glucose 300 grams daily, which is considered the standard dosage for glucose loading ^{9,10,68-70,72}. This amount is usually delivered as 3 liters of 10% glucose infused daily for 4 days or longer. Although larger daily amounts are sometimes recommended, this results in larger volumes of intravenous fluid and increased risk for fluid overload and hyponatremia.

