6.2.1.2 Other clinical information

Use of Panhematin[™], glucose loading and potent opioid agonists since the last visit including the generic and trade names, dose, route of administration and time of each dose will be recorded.

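### The supportive treatment-use analysis in 12.3 leaves out glucose, a permitted and recorded attack treatment, and makes no use of the opioid baseline collected at Visit 1

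*Combined protocol and SAP*

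**What the plan says.** Section 12.3 plans a between-arm comparison of hemin use and "opioids for treatment of porphyria symptoms during the 4 weeks following treatment will be analyzed by exact two sample Wilcoxon tests"; Fisher's exact test is named as the alternative. It does not say which test goes with which measure, or whether use means any use, number of doses or amount. Glucose is not named.

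Elsewhere the protocol treats glucose as an attack treatment. Section 5.4 states: "Glucose loading will be permitted for treatment of acute attacks during the study at the discretion of the patient's physician". Section 3.2 names glucose alongside hemin as treatment for attacks during the study. Section 6.2.1.2 records hemin together with "glucose loading and potent opioid agonists since the last visit".

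On opioids, Visit 1 (6.1.1) collects "Use of opioid agonists during the previous 6 months", and concomitant medications are recorded at Visits 1 and 2. Section 3.3 records symptomatic treatment of attacks, including opioids, and adds: "Use of medications needed to control chronic symptoms, including pain, will also be recorded". Section 12.3 uses neither the history nor the chronic-medication record.

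Sections 5.3 and 5.6 set a rule for attacks that must be treated within 12 hours of the study infusion. The first attack infusion is blinded. It is hemin "if the patient was randomized to placebo, and will be placebo if the patient was randomized to" hemin.

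**The concern.** Section 3.2 describes porphyria symptoms as variable and subjective. A comparison of treatment given is therefore a useful support for an attack endpoint based on symptoms and signs. Three features weaken it.

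- **Glucose.** Home attacks are managed as the patient's own physicians judge best (5.6), so the choice between glucose and hemin lies outside the trial's control. Three attack treatments are recorded together and only two are analysed.
- **Opioids.** Section 1.1 notes that some patients have lasting symptoms, including pain. Opioids for that pain can be read as use for porphyria symptoms, and no rule separates them from opioids given for an attack. A patient on a stable opioid would then show use whether or not an attack occurs.
- **Early attacks.** If active hemin doses are counted, the 12-hour rule gives the placebo arm one dose that the hemin arm does not get, by design and not by need.

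At stake is the sensitivity of a supportive comparison in about 20 patients, where there is little information to spare.

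**Working it through.** **1. Inputs from the plan.** "All tests for significance will be two sided at the 5% significance level" (12.3). Section 12.4 supposes 10 patients per group, "if the probabilities of recurrence are 0.8 and 0.2 in the control and treatment groups respectively", and states 80% power.

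**2. The plan's own figure.** Pooled normal approximation:

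power = Φ{[|p1 − p2| − 1.96·√(2p̄(1 − p̄)/n)] / √([p1(1 − p1) + p2(1 − p2)]/n)}

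With p1 = 0.8, p2 = 0.2, p̄ = 0.5, n = 10: (0.6 − 1.96 × 0.2236)/0.1789 = 0.904, and Φ(0.904) = 0.817. The stated 80% reproduces. It belongs to the attack comparison; the plan gives no power for the treatment-use analysis. With Fisher's exact test, which 12.3 names for treatment use, the same rates give 0.635. That is the reference value below.

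**3. Any use, yes or no.** Let g be the share of attacks treated with glucose and neither hemin nor an opioid, and b the share of patients with background opioid use that gets counted, independent of attacks. Neither is in the documents; both are assumed. For attack probability p:

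P(any counted use) = 1 − [1 − p(1 − g)](1 − b)

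The expected difference between arms is 0.6(1 − g)(1 − b). It shrinks toward zero and favours neither arm.

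| g | b | placebo | hemin | Fisher power, 10 per arm |
|---|---|---|---|---|
| 0 | 0 | 0.80 | 0.20 | 0.64 |
| 0.1 | 0 | 0.72 | 0.18 | 0.51 |
| 0.2 | 0 | 0.64 | 0.16 | 0.40 |
| 0.3 | 0 | 0.56 | 0.14 | 0.30 |
| 0 | 0.1 | 0.82 | 0.28 | 0.51 |
| 0 | 0.3 | 0.86 | 0.44 | 0.30 |
| 0 | 0.5 | 0.90 | 0.60 | 0.15 |
| 0 | 0.7 | 0.94 | 0.76 | 0.04 |
| 0.2 | 0.3 | 0.75 | 0.41 | 0.16 |

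If hemin is analysed alone, the relevant share is attacks treated without hemin. At 25% the rates are 0.60 and 0.15 (power 0.35); at 50% they are 0.40 and 0.10 (power 0.15).

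**4. Amount of opioid, Wilcoxon test.** A simulation used 10 per arm, attack rates 0.8 and 0.2, and 3,000 trials per setting. Chronic users took a lognormal amount (median 60 units/day, log SD 0.7) for 28 days with 5% within-patient noise. An attack added 4 days (median 60 units/day, log SD 0.5). All of these amounts are assumptions.

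| chronic users | total 4-week use | change from baseline | attack opioids only |
|---|---|---|---|
| none | 72% | – | – |
| 30% | 22% | 62% | 72–73% |
| 50% | 9% | 56% | 72–73% |

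The gain from a baseline depends on how stable chronic use is. In repeat runs at 30% chronic users, change from baseline gave 57% against 20% for total use with 5% noise, and 33% against 23% with 30% noise. The direction held; the size did not.

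**5. The 12-hour rule.** It shifts a count of active doses by one per affected patient. If use is scored yes or no and open-label hemin follows, the shift disappears. It applies only to attacks that need treatment within 12 hours.

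**The case against.** The strongest reply is that 12.3 already limits opioids to use for porphyria symptoms, while 3.3 records attack treatment and chronic medication as separate items. If only attack opioids are counted, chronic use costs nothing: simulated power stays at 72–73%. This stands against any claim that the plan analyses total opioid use. It does not close the gap, because chronic porphyria pain fits the wording and no separating rule is given.

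Second, attacks treated with glucose alone may be few. Enrolled patients are already on hemin, on-site attacks are treated with hemin (5.6), past attacks should have included pain severe enough for a narcotic (2.1), and 1.3 credits glucose only with sometimes helping in mild attacks. An attack treated with glucose plus an opioid still registers on the opioid measure. This is fair, and it is why no single power loss can be asserted.

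Third, the remedy is imperfect. The Visit 1 entry lists no dose or frequency and may include opioids from earlier attacks. Dose and time are specified only at follow-up, and there for potent opioids.

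A reader might infer that the trial misses treated attacks. It does not: the primary variable is an attack defined by symptoms and signs (2.1), whatever treatment was given. A reader might also infer that background opioids overwhelm the comparison or bias it toward one arm. The documents give no prevalence, and under blinded randomisation the expected effect is dilution, with chance imbalance possible at 10 per arm.

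**Conclusion.** The point holds as a minor gap in a supportive analysis. The text alone establishes two things: glucose is permitted and recorded but not analysed, and opioid baseline data are collected but not used. Both can only weaken the comparison. How much depends on two rates that the documents do not give, so the power figures are ranges under assumptions and not estimates for this trial. The 12-hour rule matters only if active doses are counted, and then rarely.

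The primary logistic regression and the sample size are untouched, and treatment use is not listed among the efficacy variables in 12.2.1. Because 5.6 declines to call treatment of attacks rescue, attack treatment is the better term.

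**What to change.** In 12.3:

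1. Define attack treatment as any non-prophylactic hemin, glucose loading, or new or increased opioid use for porphyria symptoms during the 4 weeks, and compare it between arms by Fisher's exact test.
2. Analyse opioid use as attack-related use above the patient's pre-infusion regimen, taken from the concomitant medications at Visits 1 and 2 with the 6-month opioid history as support. Alternatively, adjust for baseline opioid use. State the measure (any use, doses or amount) to which the Wilcoxon test applies.
3. Count the blinded first attack infusion under 5.3 and 5.6 as one attack treatment in both arms, whatever it contained.

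The cost is SAP wording and some data handling. No visit, test or clinical management changes. The drawback is the weak baseline opioid record: if no daily amount can be derived from it, new or increased use (yes or no) or a baseline-use indicator is the workable version.
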